3.2 Population

Men and women aged from 18 years (inclusive) and older with a confirmed diagnosis of moderate to severe plaque psoriasis (lasting for at least 6 months before signing the ICF) who did not respond to/are candidates for systemic therapy including TNF- α inhibitors or UV therapy.

4. EVALUATION CRITERIA

4.1 Efficacy endpoints

Primary endpoint

- Proportion of patients who achieved PASI 75 at Week 12, by study arms.

Secondary endpoints in the main treatment period (Week 0 to Week 54):

- Proportion of patients who achieved PASI 75/90/100 at Weeks 8, 16, 24, 42 and 52, by study arms.
- Proportion of patients with sPGA score 0 or 1 at Weeks 8, 12, 16, 24, 42, and 52.
- Proportion of patients with sPGA score 0 at Weeks 16, 24, 42, and 52.
- Relative change from baseline in PASI score at Weeks 8, 12, 16, 24, 42 and 52.
- Change from baseline in itch severity measured with visual analog scale (VAS) (0 mm to 100 mm) at Weeks 1, 12, 24, and 52.
- Change from baseline in Nail Psoriasis Severity Index (NAPSI) score at Week 12, 24, and 52.
- Change from baseline in Dermatology Life Quality Index (DLQI) score at Weeks 8, 12, 24, 42, and 52.
- Proportion of patients with DLQI score 0 or 1 at Weeks 24, 42, and 52.

- Proportion of patients (among those with psoriatic arthritis) who achieved an ACR20/50/70 at Weeks 12, 24, and 52.

Secondary endpoints during the extension study period (Week 54 through Week 166):

- Proportion of patients who maintained PASI 75/90/100 response after 62, 74, 86, 98, 110, 122, 134, 146, and 154 weeks of treatment vs. response after 52 weeks of treatment with BCD-085.
- Proportion of patients who maintained sPGA 0-1 response after 62, 74, 86, 98, 110, 122, 134, 146, and 154 weeks of treatment vs. response after 52 weeks of treatment with BCD-085.
- Proportion of patients who maintained sPGA score 0 response after 62, 74, 86, 98, 110, 122, 134, 146, and 154 weeks of treatment vs. response after 52 weeks of treatment with BCD-085.
- Proportion of patients who maintained DLQI score 0-1 after 62, 74, 86, 98, 110, 122, 134, 146, and 154 weeks of treatment vs. response after 52 weeks of treatment with BCD-085.
- Time to loss of PASI 75/90/100, sPGA 0-1/sPGA 0, DLQI 0-1 response during the treatment with BCD-085.
- Proportion of patients who maintained ACR 20/50/70 response (among patients with psoriatic arthritis) after 62, 74, 86, 98, 110, 122, 134, 146, and 154 weeks of treatment vs. response after 52 weeks of treatment with BCD-085.
- Proportion of patients who achieved PASI 75/90/100 response after 62, 74, 86, 98, 110, 122, 134, 146, and 154 weeks of treatment with BCD-085.
- Proportion of patients with sPGA score 0 or 1 after 62, 74, 86, 98, 110, 122, 134, 146, and 154 weeks of the treatment with BCD-085.
- Proportion of patients who achieved sPGA score 0 after 62, 74, 86, 98, 110, 122, 134, 146, and 154 weeks of treatment with BCD-085.
- Change from baseline in itch severity measured with visual analog scale (VAS) (0 mm to 100 mm) after 62, 74, 86, 98, 110, 122, 134, 146, and 154 weeks of treatment with BCD-085.
- Change from baseline in Nail Psoriasis Severity Index (NAPSI) score after 62, 74, 86, 98, 110, 122, 134, 146, and 154 weeks of treatment with BCD-085 (among patients with nail psoriasis at baseline).
- Proportion of patients who achieved DLQI score 0 or 1 after 62, 74, 86, 98, 110, 122, 134, 146, and 154 weeks of treatment with BCD-085.

- Change from baseline in Dermatology Life Quality Index (DLQI) score after 62, 74, 86, 98, 110, 122, 134, 146, and 154 weeks of treatment with BCD-085.

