**Procedures of Visit 2 (Day 1 of Week 1), performed 7 days after the first injection of BCD-085/placebo**

- Physical examination.
- The patient fills out the VAS for itch.
- Administration of BCD-085/placebo.
- Blood pressure, heart rate and body temperature (immediately after dosing).
- Information about concomitant therapy.
- Assessing injection site reactions.
- Recording AEs/SAEs.

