3. STUDY DESIGN

3.1 Design

The BCD-085-7 study is an international multicenter, randomized, double-blind, placebo-controlled clinical study to evaluate the efficacy and safety of two dosing regimens of BCD-085 (JSC BIOCADC, Russia) in patients with moderate to severe plaque psoriasis (Phase III).

The study is planned to enroll 213 adult patients with moderate to severe plaque psoriasis (diagnosed at least 6 months before signing the informed consent form) who have BSA $\geq 10\%$, PASI score ≥ 10 , and sPGA score ≥ 3 .

Before being screened for the study, patients must read and sign the informed consent form and undergo a screening examination (within 28 calendar days) to confirm that they are eligible for the study. The Protocol does not provide any additional requirements regarding the diet or physical activity during the screening or study period.

Stratification and randomization

When the Investigator has decided that the patient can take part in the study, the patient should be stratified according to his/her body weight (<100 kg/ ≥ 100 kg), previous use of monoclonal antibodies for the treatment of psoriasis (previously treated/naive), PASI score (<20 / ≥ 20), and psoriatic arthritis (yes/no) and randomized at a 2:2:1 ratio to one of the three study groups: 1) BCD-085 Q2W (Arm 1), 2) BCD-085 Q4W (Arm 2), 3) placebo (Arm 3).

Study periods

1. Screening (up to 28 days from signing the Patient Information Sheet with the Informed Consent Form, inclusive).
2. Main treatment period (from Week 0 through Week 54, inclusive).
3. Extension treatment period:
 - 1) for Arms 1 and 2: from Week 54 through Week 154,
 - 2) for Arm 3: from Week 54 through Week 166.
4. Follow-up period:
 - 1) for Arms 1 and 2: from Week 154 through Week 158,
 - 2) for Arm 3: from Week 166 through Week 170.

Screening period:

Up to 28 days from signing the Patient Information Sheet with the Informed Consent Form, inclusive.

Main treatment period (Week 0 through Week 54):

In this study period patients will be distributed to three arms:

- **Arm 1:** Patients in this arm (85 subjects) will receive BCD-085 120 mg (two subcutaneous injections, 60 mg in 1.0 mL each) once a week during the first 3 weeks (induction) and then once every 2 weeks through Week 10. Thus, the investigational product will be administered on Day 1 of Week 0, Week 1, Week 2, Week 4, Week 6, Week 8, and Week 10.

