- **Arm 2:** Patients in this arm (85 subjects) will receive BCD-085 120 mg (two subcutaneous injections, 60 mg in 1.0 mL each) once a week during the first 3 weeks (induction) and then once every 4 weeks through Week 10. Thus, the investigational product will be administered on Day 1 of Week 0, Week 1, Week 2, Week 6 and Week 10. To maintain the study blind, patients of this arm will receive placebo (2 injections) on Day 1 of Week 4 and Week 8.
- **Arm 3:** Patients of this arm (43 subjects) will receive placebo (2 subcutaneous injections of placebo, 1.0 mL each) on Day 1 of Week 0, Week 1, Week 2, Week 4, Week 6, Week 8 and Week 10.

On Week 12, the treatment efficacy will be assessed with a PASI 75 score, and the treatment will be **unblinded**. Patients from Arms 1 and 2 will be given BCD-085 once every 4 weeks. Patients from Arm 3 will receive BCD-085 as follows:

- ✓ Induction: Weeks 12, 13, and 14, once a week;
- ✓ Weeks 18 through 50: once every 4 weeks.

Therefore, there will be 3 arms even after unblinding, and patients will receive BCD-085 according to the regimens described below:

- a) Patients in Arm 1 will receive BCD-085 120 mg (2 subcutaneous injections of 60 mg each) once every 4 weeks starting from Week 14 through Week 50.
- b) Patients in Arm 2 will receive BCD-085 120 mg (2 subcutaneous injections of 60 mg each) once every 4 weeks starting from Week 14 through Week 50.

c) Patients in Arm 3 will receive BCD-085 120 mg once a week at Weeks 12, 13, 14, then once every 4 weeks (Weeks 18, 22, 26, 30, 34, 38, 42, 46, 50).

Extension study period (from Week 54 through Week 154 for Arms 1 and 2, through Week 166 for Arm 3):

During **the extension study period** all patients who achieved PASI 75 at Week 52 will receive BCD-085 120 mg once every 4 weeks:

- a) Patients from Arm 1 will receive BCD-085 from Week 54 through Week 154.
- b) Patients from Arm 2 will receive BCD-085 from Week 54 through Week 154.
- c) Patients from Arm 3 will receive BCD-085 from Week 54 through Week 166.

Patients who failed to achieve PASI 75 at Week 52 will be withdrawn from the study.

In Arm 3, treatment will be extended by 12 weeks so that the total treatment duration in all arms can be 154 weeks. During the main treatment period (during the first 12 weeks of the study), patients from Arm 3 receive placebo, so the treatment period for these patients is extended to 166 weeks.

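### For itch at Week 1 the SAP does not pool the two BCD-085 arms, although their treatment is identical until Week 4; pooling would cut the standard error against placebo by 8.8%

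*SAP*

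**What the plan says.** **Endpoint.** SAP 4.1 lists "Change from baseline in itch severity measured with visual analog scale (VAS) (0 mm to 100 mm) at Weeks 1", and then at Weeks 12, 24 and 52, among the secondary endpoints of the main treatment period. This line does not itself mention study arms, whereas the two PASI 75 lines in that period do.

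**Dosing (SAP 3.1).** In Arm 1 the product is "administered on Day 1 of Week 0, Week 1, Week 2, Week 4, Week 6, Week 8, and Week 10". In Arm 2 it is "administered on Day 1 of Week 0, Week 1, Week 2, Week 6 and Week 10", and "patients of this arm will receive placebo (2 injections) on Day 1 of Week 4 and Week 8" to keep the blind. The dose is 120 mg in both arms.

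**Timing.** Protocol 4.6.2 describes Visit 2 as "performed 7 days after the first injection of BCD-085/placebo" and lists the itch VAS before that day's injection.

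**Analysis.** SAP section 5 says the 12-week report gives efficacy and safety results by study arm. SAP 8.2 places itch change among the quantitative variables and offers a general set of tests: Student's and Welch's t-tests and ANOVA, or Mann-Whitney, Wilcoxon, Kruskal-Wallis and Friedman tests. It adds a Benjamini-Yekutieli correction without saying which tests form the family. No section defines a pooled BCD-085 arm, and SAP section 9 plans no further analyses.

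**The concern.** At Week 1 the trial has three randomised groups but only two treatments. An analysis by arm keeps the identically treated patients apart and sets each half against the small placebo group, which gives away precision.

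The endpoint has some interest of its own. Week 1 itch is the earliest efficacy assessment in SAP 4.1; every other efficacy endpoint starts at Week 8 or later.

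Interpretation is also at stake. If Q4W and Q2W were compared at Week 1, any difference would be chance. The trial's main hypothesis concerns those two regimens, so a chance difference could be taken for a regimen effect.

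**Working it through.** **1. Are the arms identical at Week 1?** Set the two schedules side by side:

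| Week | 0 | 1 | 2 | 4 | 6 | 8 | 10 |
|---|---|---|---|---|---|---|---|
| Arm 1 | active | active | active | active | active | active | active |
| Arm 2 | active | active | active | placebo | active | placebo | active |

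The first difference is at Week 4. When the Week 1 VAS is completed, both arms have had one 120 mg dose. If a site completed the VAS after the Week 1 injection, both would have had two, so the order within the visit does not matter. Treatment is blinded until Week 12 (Protocol 4.3.5), so knowledge of the regimen should not separate the arms either. The true Arm 1 minus Arm 2 difference at Week 1 is zero by design.

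**2. The plan's own figures.** The plan gives no precision, SD or expected effect for itch. Its group sizes come from PASI 75 at Week 12. With rates 0.891 and 0.826, margin 0.2038 (Protocol 9.3.1) and one-sided 0.05:

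n = (0.891 × 0.109 + 0.826 × 0.174) × (1.645 + 0.842)² / (0.2038 − 0.065)² = 77.3 per active arm,

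close to the stated 77. Then 77 × 1.1 = 84.7 and 39 × 1.1 = 42.9 give the planned 85 and 43. Only these group sizes carry over to the itch calculation.

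**3. Standard error of active minus placebo**, in units of the SD of itch change, assumed equal in all groups: SE = √(1/n_active + 1/n_placebo).

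- One arm versus placebo: √(1/85 + 1/43) = 0.187.
- Both arms pooled versus placebo: √(1/170 + 1/43) = 0.171.
- SE ratio: 0.1707 / 0.1871 = 0.912, a fall of 8.8%.
- Information ratio: (0.1871 / 0.1707)² = 1.20.

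With the evaluable numbers 77/77/39 the SEs are 0.197 and 0.179, and the fall is again 8.8%.

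**4. What this means for power.** At two-sided 0.05, the smallest effect detectable with 80% power is (1.960 + 0.842) × SE: 0.524 SD for one arm and 0.478 SD pooled. Because the documents give no SD or expected effect for itch, the effects below are assumptions, shown as a range (85/85/43, no multiplicity correction):

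| Assumed true effect (SD) | Power, one arm vs placebo | Power, pooled vs placebo |
|---|---|---|
| 0.3 | 0.361 | 0.420 |
| 0.4 | 0.570 | 0.649 |
| 0.5 | 0.762 | 0.834 |
| 0.6 | 0.894 | 0.940 |

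The gain is about 5 to 8 percentage points over this range.

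**The case against.** The strongest reply is that the plan contains no written error here. No section names an Arm 1 versus Arm 2 test of itch at Week 1. SAP section 5 describes what a report will contain, SAP 8.2 is a general menu, and Protocol 9.1 leaves the choice of method until the data are collected. This stands, and it limits the point. A reader might infer that the plan tests a difference that cannot exist, or that pooling reduces three pairwise tests to one. The documents support neither, because they do not list the pairwise contrasts. They support only that efficacy is analysed by arm and that no pooled arm is defined.

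A reader might also infer a definite saving under the Benjamini-Yekutieli correction. That cannot be quantified. If the family covers many endpoints and visits, dropping a contrast changes little; if it is formed per endpoint and visit, it changes more. The SAP does not say which.

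It is also fair that importance is limited. The main-period efficacy objectives concern results after 12 and 52 weeks, and none concerns onset. The schedules are set out in the SAP, so a careful reader could see that a regimen difference at Week 1 is chance.

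Finally, one could prefer the same by-arm contrasts at every visit, in line with the aim of comparing Q4W, Q2W and placebo. That is a legitimate preference, but showing by-arm values descriptively at Week 1 keeps the series intact while the formal comparison uses all active patients.

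**Conclusion.** The point holds as an efficiency improvement. For change in itch VAS at Week 1, comparing each BCD-085 arm separately with placebo gives a standard error of 0.187 SD where 0.171 SD is available. Pooling is unbiased at that visit because treatment is identical until Week 4, and it leaves no reason for a Q4W versus Q2W contrast there.

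The 8.8% rests on the planned group sizes and a common SD; the power figures rest in addition on assumed effects of 0.3 to 0.6 SD. The gain is modest and confined to one secondary endpoint at one visit. The argument does not carry over to itch at Week 12 or later, after the arms have diverged. The by-arm analysis is not biased, and the primary endpoint and sample size are untouched.

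**What to change.** Add one sentence to SAP 8.2: for change from baseline in itch VAS at Week 1 only, the inferential comparison is Arms 1 and 2 pooled versus placebo, with results by arm shown descriptively; from Week 12 on, the comparison is by arm.

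This needs no extra patients, visits or data. The only cost is that itch has a different formal contrast at Week 1 from the later visits, which the sentence itself explains. It should be settled before treatment is unblinded at Week 12; a pooled analysis added after that should be labelled post hoc.

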4.2. Safety endpoints

- Proportion of patients who developed AEs/SAEs.
- Proportion of patients who developed injection site reactions.
- Proportion of patients who developed Grade 3/4 AEs/SAEs.
- Proportion of patients who discontinued the study due to AEs and/or SAEs.
- Exposure adjusted incidence rate of AEs/SAEs during the extension study.

4.3. Immunogenicity endpoints

- Proportion of patients with anti-drug antibodies (binding/neutralizing).

5. THE PLANNED ANALYSIS

Final report

The final report will contain results of the efficacy and safety endpoint analysis by study arms after the 12-week blinded treatment period (Week 0 to Week 12) in 213 study subjects.

Supplementary reports

Supplementary Report 1 will contain results of the efficacy and safety endpoint analysis by study arms after 54 weeks of the study.

Supplementary Report 2 will contain results of the efficacy and safety endpoint analysis after 2 years of the study treatment (110 weeks in patients from Arms 1 and 2, 122 weeks in patients from Arm 3).

Supplementary Report 3 will contain results of the efficacy and safety endpoint analysis after 3 years of the study treatment (158 weeks in patients from Arms 1 and 2, 170 weeks in patients from Arm 3).

6. SAMPLE SIZE CALCULATION

Two independent hypotheses will be tested one after another:

1. The main study hypothesis (stating the non-inferiority of BCD-085 Q4W vs. BCD-085 Q2W) will be tested at the significance level of 0.05;

2. The hypothesis stating the superiority of BCD-085 in different dosing regimens over placebo will be tested at the significance level of 0.05.

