**Immunogenicity:**

- Proportion of patients with anti-drug antibodies (binding/neutralizing)

will be processed using the frequency tables, Fisher's test,  $\chi^2$  test, and Cochran-Mantel-Haenszel test. The categorical data will be described using percentages or proportions.

For multiple comparisons, the Benjamini-Yekutieli procedure will be used. Regression will be used to assess the effects of the factors other than the therapy type. Time to loss of response will be assessed using log-rank test, Kaplan-Meier curves, and Cox regression model. Time will be counted from the response during the treatment with BCD-085. Right censoring can be used to analyze time to events.

Statistical methods will be chosen based on the type and distribution of raw data. Applicability of certain statistical tests will be evaluated after all the data are collected because it is impossible to predict the distribution pattern, data homogeneity and other data characteristics in advance.

The data will be processed using programming language R for statistical processing and SAS 9.4 software environment.

Translated from Russian to English, dated 26-Nov-2019

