## 9.2. Statistical analysis steps and timelines for reports

### 9.3. Planned number of subjects. Justification of sample size, including reasoning or calculations to justify statistical power, and clinical justification of the study

Two independent hypotheses will be tested during the study:

1. The main study hypothesis (stating the non-inferiority of BCD-085 Q4W vs. BCD-085 Q2W) will be tested at the significance level of 0.05;
2. The hypothesis stating the superiority of BCD-085 in different dosing regimens over placebo will be tested at the significance level of 0.05.

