8.2. Description of the Statistical Methods to be Employed

The statistical analysis will be performed using two-sided hypothesis tests. The statistical significance level is 0.05.

The study hypothesis of non-inferior efficacy of BCD-085 once every 4 weeks vs. BCD-085 once every 2 weeks will be proved by comparing the lower bound of the 95% confidence interval for the difference in proportions of patients with PASI 75 at Week 12 between the BCD-085 Q4W and BCD-085 Q2W with pre-specified non-inferiority margin (δ) equal to -20.38%.

The hypothesis stating the superior efficacy of BCD-085 over placebo will be proved by comparing the lower bound of the 95% confidence interval for the difference in proportions of patients with PASI 75 by Week 12, in each BCD-085 arm and placebo arm, with pre-specified non-inferiority margin (δ , 0%).

Quantitative Data

The following quantitative data will be analyzed in the study:

Efficacy:

- Relative PASI change,
- Change in itch severity (VAS, 0 to 100 mm),
- Change in NAPSI score,
- Change in quality of life according to the DLQI score,

- Time to loss of PASI 75/90/100, sPGA 0-1/sPGA 0, DLQI 0-1 response during the treatment with BCD-085,

Safety:

- CBC results,
- Blood chemistry results,
- Vital signs,

Demographics and other baseline characteristics:

- General information (age, body weight, height, BMI),
- Duration of the disease, severity and the area of psoriasis (PASI), BSA, severity by sPGA, severity of nail psoriasis (NAPSI), severity of pruritus (VAS), quality of life score (DLQI), the presence of depression (Beck's score), functional activity (HAQ-DI), tender joint count (of 68), swollen joint count (of 66).

Quantitative data will be described using the following descriptive statistics: mean, SD, median, quartiles, CV, min, and max.

Quantitative variables will be tested for normality using the Shapiro-Wilk test.

Normally distributed quantitative variables will be tested using the two-sample Student's t-test, Welch's t-test, and ANOVA.

Non-normally distributed quantitative variables will be tested using the Mann-Whitney U-test, the Wilcoxon test, the Kruskal-Wallis test, and the Friedman test.

Time to loss of response will be assessed using log-rank test, Kaplan-Meier curves, and Cox regression model. Time will be counted from the response during the treatment with BCD-085. Right censoring can be used to analyze time to events.

Categorical Data

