The following categorical data will be analyzed in the study:

Efficacy:

- Proportion of patients with PASI 75/90/100,
- Proportion of patients with sPGA score 0 or 1,
- Proportion of patients with DLQI score 0 or 1,
- Proportion of patients (among patients with psoriatic arthritis) who achieved an ACR20/50/70,
- Proportion of patients who maintained PASI 75/90/100 score,
- Proportion of patients who maintained sPGA score 0 or 1,

- Proportion of patients who maintained DLQI score 0 or 1,
- Proportion of patients who maintained ACR 20/50/70 response (among patients with psoriatic arthritis).

Safety:

- Proportion of patients who developed AEs/SAEs,
- Proportion of patients who developed injection site reactions,
- Proportion of patients who developed Grade 3/4 AEs/SAEs,
- Proportion of patients who discontinued the study due to AEs and/or SAEs,
- Exposure adjusted incidence rate of AEs/SAEs during the extension study.

Immunogenicity:

- Proportion of patients with anti-drug antibodies (binding/neutralizing).

Demographics and other baseline characteristics:

- General information (Race, Sex, Childbearing potential (women)),
- Prior therapies for plaque psoriasis,
- Co-morbidities and the most relevant prior diseases,
- Medical history.

Extent of exposure:

- The number of administrations given during the study,
- Exposure of BCD-085 with mean daily dose and treatment duration.

Percentages or proportions will be used to describe categorical data.

Categorical data will be processed using frequency tables, the Fisher's exact test, Yates-corrected Pearson's χ^2 test, and the Cochran-Mantel-Haenszel test.

The Benjamini-Yekutieli correction for multiple testing will be used.

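### Non-inferiority of Q4W to Q2W is listed first and as independent of superiority over placebo; a superiority-first order would be a free safeguard, and the Benjamini-Yekutieli scope needs its own sentence.

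*SAP*

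**What the plan says.** SAP section 6 opens with "Two independent hypotheses will be tested one after another". First comes: "The main study hypothesis (stating the non-inferiority of BCD-085 Q4W vs. BCD-085 Q2W) will be tested at the significance level of 0.05". Second comes: "The hypothesis stating the superiority of BCD-085 in different dosing regimens over placebo will be tested at the significance level of 0.05". Protocol 9.3 has "Two independent hypotheses will be tested during the study" and the same two items, without the words on sequence. Neither document says what happens to the second test if the first fails, whether both must succeed, or how the overall type I error is controlled.

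SAP 8.2 says "The statistical analysis will be performed using two-sided hypothesis tests" at level 0.05. It decides non-inferiority by "comparing the lower bound of the 95% confidence interval for the difference in proportions of patients with PASI 75 at Week 12" with the margin of -20.38%, and superiority by the same kind of bound against 0 for each regimen. These intervals carry no adjustment.

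SAP 8.2 also closes its categorical-data part, whose endpoint list includes PASI 75, with "The Benjamini-Yekutieli correction for multiple testing will be used". Protocol 9.1 says "For multiple comparisons, the Benjamini-Yekutieli procedure will be used". Neither names a family, a number of tests or an exemption.

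SAP 6.1, under the non-inferiority heading, describes setting a margin at half the lower 95% bound of the Q2W-placebo difference. The text calls it a superiority margin, but that margin is 0 in Protocol 9.3.2 and SAP 8.2, so I read it as the source of the non-inferiority margin.

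**The concern.** The three comparisons share arms, so they are not statistically independent. More important, a margin built from the effect of Q2W over placebo has meaning only if Q2W beats placebo in this trial. The placebo arm is there to show that, but the stated order does not use it: as written, Q4W may be called non-inferior to Q2W whatever the placebo comparisons show.

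The phrase about testing one after another could also be taken as a hierarchy with non-inferiority at the top. Superiority would then be reachable only after non-inferiority, the less certain of the two claims.

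Separately, the correction sentence leaves two statisticians free to reach different primary conclusions from the same data, depending on whether they apply it to the main comparison.

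**Working it through.** **Inputs.** Design rates: Q2W 0.891, Q4W 0.826, placebo 0.039 (Protocol 9.3.1 and 9.3.2). Margin 0.2038 in absolute value (SAP 8.2). Evaluable 77/77/39, randomised 85/85/43 (SAP 6.2). Alternative placebo rate 0.2308, from 6 of 26 in Phase II (Protocol, Table 11). SAP 8.2 names no interval method; a Wald interval is assumed. A two-sided 95% interval gives one-sided 0.025.

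**The plan's own figure.** With unpooled variance, 80% power and one-sided 0.05, the non-inferiority formula gives 78 per arm against the stated 77. One-sided 0.025 gives 99. So 77 belongs to one-sided 0.05, while the analysis rule is one-sided 0.025.

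**Non-inferiority power under the SAP rule.**
- 77 per arm: SE = sqrt(0.891×0.109/77 + 0.826×0.174/77) = 0.05593. Distance to margin = 0.2038 - 0.065 = 0.1388. Ratio = 2.482. Power = Φ(2.482 - 1.960) = 69.9%.
- 85 per arm: SE = 0.05323, ratio 2.608, power = Φ(0.648) = 74.1%.

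**Cost of a superiority gate.** Superiority power exceeds 99.99% for each regimen at both sample sizes, with placebo at 3.9% or at 23.08%. In 200,000 simulated three-arm trials at the design rates, both superiority tests always passed. Non-inferiority power was 70.17% with and without the gate at 77 per arm, and 74.51% with and without it at 85. The cost is 0.0 points. A gate in the opposite direction would hold the superiority claim to the same 70% to 74%.

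**What the gate prevents.** Suppose all three arms share one response rate p, at 77/77/39. Ungated non-inferiority passes with probability Φ(0.2038/SE - 1.960), where SE = sqrt(2p(1-p)/77).

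| p | SE | 0.2038/SE | Ungated | Superiority gate |
|---|---|---|---|---|
| 0.039 | 0.0312 | 6.53 | over 99.9% | about 2.6% |
| 0.2308 | 0.0679 | 3.00 | 85% | about 1.2% |

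The gated figures come from enumerating all outcomes; simulation gave 2.7% and 1.1%. With equal rates the non-inferiority statement is literally true. The harm is a positive headline claim in a trial where nothing worked.

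**Error control.** In a fixed order, a false claim requires falsely rejecting the first true null hypothesis in the sequence, so the family-wise error is at most a nominal one-sided 2.5%. Testing the two placebo comparisons in parallel does not achieve this. Their correlation is 77/116 = 0.66. If neither regimen works, at least one passes with probability 4.3% by the normal approximation, and about 5.5% with Wald intervals at 23.08%.

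**Benjamini-Yekutieli, if it covered the three primary tests.** This family is an assumption. c = 1 + 1/2 + 1/3 = 1.833. With both superiority p-values very small, non-inferiority must meet 0.05/1.833 = 0.0273 two-sided, z = 2.208.
- 77 per arm: Φ(2.482 - 2.208) = 60.8%, down from 69.9%.
- 85 per arm: Φ(2.608 - 2.208) = 65.5%, down from 74.1%.

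Larger assumed families, with non-inferiority having the largest p-value, give 54% (10 tests) and 51% (20 tests) at 77 per arm.

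**The case against.** **The gate changes nothing that is expected to happen.** This stands. Phase II gave 92.86% against 23.08% for 120 mg, and superiority power here exceeds 99.99%. Placebo superiority is already a formal hypothesis, and all Week 12 results go into one report (SAP section 5), so non-inferiority without superiority would be visible. But visible is not the same as barred by rule.

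**A reader might infer that the plan materially inflates type I error.** The documents do not support that. When both regimens beat placebo, the only possible false primary claim is non-inferiority, at nominal 2.5% (2.7% to 2.8% simulated at the margin). A joint error near 5% needs a remote case, such as Q4W equal to placebo with Q2W 20.38 points higher.

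**Superiority may already be one joint claim.** Protocol section 3 and SAP 2.3 speak of both regimens together, which would leave two primary claims and not three. SAP 6.2, however, writes two separate null hypotheses, and no success rule settles the matter.

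**A reader might infer that the correction contradicts the primary rule.** That is too strong. SAP 8.2 gives the interval rule first, the correction acts on p-values, and its sentence follows the categorical tests. The section can be read as already exempting the primary comparisons. What remains is an ambiguity, because PASI 75 is in the categorical list and no exemption is stated.

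**Independent may simply mean separate in a translated text.** Possibly, which is a reason to replace the word.

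**Conclusion.** The point holds as a free improvement. The plan allows a non-inferiority claim that does not rest on either regimen beating placebo. With equal, ineffective arms that claim would be made in 85% to over 99.9% of trials, against about 1.2% to 2.6% with a gate. These figures assume 77/77/39 and a Wald interval.

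Three limits apply. The ordering does not settle the scope of Benjamini-Yekutieli; the loss of about 9 points rests on an assumed family of three and on a reading that the SAP does not require. No power cost means relative to 70% to 74%, not to the stated 80%; that gap comes from sizing at one-sided 0.05 and is a separate issue. The 2.5% limit is nominal: with a placebo rate of 3.9%, Q4W equal to placebo and Q2W 20.38 points higher, both placebo comparisons passed in 7.7% of simulated Wald trials at 77/77/39, so the interval method matters.

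**What to change.** In SAP 6 and 8.2 and Protocol 9.3, state that the primary tests run in this order, each by the lower bound of the two-sided 95% interval and each only if the previous one succeeds:
1. Q2W vs placebo, bound above 0.
2. Q4W vs placebo, bound above 0.
3. Q4W vs Q2W, bound above -20.38%.

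An equivalent choice is to define superiority as one joint claim for both regimens, followed by non-inferiority. Replace the word independent, and name the interval method.

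In a separate sentence in SAP 8.2 and Protocol 9.1, say that Benjamini-Yekutieli does not apply to these three tests, and list the secondary endpoints and time points that it covers. It controls the false discovery rate, not the family-wise error rate, and the text should say so.

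The cost is wording only: no patients and no loss of power. The text should be settled before the Week 12 comparison is run, so that neither the order nor the scope can look chosen from the data.
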